4 OBJECTIVES AND ENDPOINTS

Key study definitions are provided below.

Clinical remission	CDAI < 150
Clinical response	A reduction from baseline in the CDAI score of ≥ 100 points or a total CDAI score < 150
Endoscopic response	$\geq 50\%$ improvement from baseline in the SES-CD
[REDACTED]	[REDACTED]
[REDACTED]	[REDACTED]
[REDACTED]	[REDACTED]
[REDACTED]	[REDACTED]
PRO2 remission	Average daily score for abdominal pain ≤ 1 and average number of very soft (loose) or liquid (watery) stools (BSS Type 6 or 7 only) ≤ 3 on the PRO2 and both not worse than baseline
[REDACTED]	[REDACTED]
[REDACTED]	[REDACTED]
[REDACTED]	[REDACTED]

BSS = Bristol Stool Scale; CD = Crohn’s Disease; CDAI = Crohn’s Disease Activity Index; [REDACTED]; PRO2 = patient (or subject) reported outcome based on the stool frequency and abdominal pain components of the CDAI; SES-CD = Simple Endoscopic Score for Crohn’s Disease.

[REDACTED]

Safety endpoints and primary, secondary, and exploratory efficacy endpoints are specified below. Additional endpoints may be specified in the statistical analysis plan (SAP).

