6.1 Inclusion Criteria

1) Signed Written Informed Consent

- a) Willing to participate in the study and sign the ICF.
- b) Willing and able to complete all study-specific procedures and visits.

2) Type of Subject and Target Disease Characteristics

- a) Not applicable per Global Revised Protocol v3.0
- b) Not applicable per Global Revised Protocol v3.0
- c) Not applicable per Global Revised Protocol v3.0
- d) Not applicable per Global Revised Protocol v3.0
- e) Documented diagnosis of CD for at least 3 months prior to screening, including ileal, colonic, or ileo-colonic disease distribution, confirmed by:
 - ◆ Source: Medical records with report of a colonoscopy with ileal intubation (ileocolonoscopy), which shows features consistent with CD, as determined by the procedure performing physician, AND
 - ◆ Source: Medical record documentation of a histopathology report showing features consistent with CD, as determined by the local pathologist.

Note: If a histopathology report is not available, histologic samples can be obtained at the screening endoscopy and sent to a local laboratory to confirm diagnosis of CD before proceeding to randomization. The screening endoscopy must show features consistent with CD.

- f) Must have active moderate to severe CD, as defined by:
 - CDAI score of 220 to 450 AND
 - PRO2: Average daily score for abdominal pain ≥ 2 OR average daily number of very soft (loose) or liquid (watery) stools (BSS Type 6 or 7 only; XXXXXXXXXX ≥ 4 , (see [Section 9.1](#)), AND
 - Evidence of active inflammation in at least 1 of the 5 ileocolonic segments (based on central reading) with total SES-CD ≥ 6 or SES-CD ≥ 4 if only isolated ileitis is present on baseline endoscopy

- g) Must have had an inadequate response, LOR, or intolerance to a standard treatment course of 1 or more of the following medications as below:
- Oral 5-ASAs: (eg, mesalamine, sulfasalazine, olsalazine, balsalazine) at or above the approved label dose (or per local standard of care) for induction therapy for at least 6 weeks
 - Oral corticosteroids: Prednisone \geq 40 mg/day or equivalent for 2 weeks, or 2 failed attempts to taper oral corticosteroids below prednisone or equivalent 10 mg daily, or a relapse within 3 months of discontinuing corticosteroids
 - Intravenous (IV) corticosteroids: hydrocortisone \geq 400 mg/day or equivalent for at least 1 week

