7.2 Method of Treatment Assignment

At the time of the screening visit, immediately after informed consent is obtained and before any study-related procedures are performed, the investigative site will access the interactive response technology (IRT) for assignment of the subject identification number. This number will be unique across all sites. All enrolled subjects, including those not randomized or dosed, will be assigned sequential subject numbers. The subject number may not be used for any other subject. If a potential subject is rescreened, they will be given a new identification number.

Eligible subjects will be centrally randomized using IRT to receive oral treatment during the Induction Period with BMS-986165 at 6 mg BID or 3 mg BID or placebo BID, according to a computer-generated block randomization scheme and in accordance with stratification criteria. Randomization numbers will be assigned prior to dosing ([Section 5.1](#)).

Before the study is initiated, each user (at investigative sites) will receive log-in information and directions on how to access the IRT. Study treatment will be dispensed at study visits as shown in [Section 2](#) (Schedule of Activities).

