9.1 Efficacy Assessments

Every effort must be made to ensure that the same evaluator(s) complete the assessment for each subject. If the evaluator(s) is unable to complete the evaluation, then a qualified individual with overlapping experience may perform the evaluation. Documentation of who performed the evaluation is to be recorded in source documents. Assessments are to be performed at approximately the same time of day throughout the duration of the study.

Baseline assessments must be performed per protocol (standard of care assessments may not be used for baseline). Procedures not specified in the protocol that are part of standard care may be performed if they do not interfere with study procedures; any data arising from such procedures are not to be reported in the eCRF.

The following procedures or tools will be used to assess subjects' CD activity during the study (see schedule in [Section 2](#)):

- CDAI^{10,15,16} ([APPENDIX 10](#)) and PRO2¹² ([REDACTED]): The CDAI and PRO2 scores will be calculated using 7 days of subject diary entries. CDAI also includes additional components, as outlined in [APPENDIX 10](#). The following rules apply to the calculation of CDAI and PRO2 scores:

For Week 0, if there are < 14 days between the endoscopy date and the visit date, the bowel preparation day will serve as the diary reference point; if there are ≥ 14 days between the endoscopy date and the visit date, the Week 0 visit date will serve as the diary reference point.

- The collection window for subject diary data used for the calculation of CDAI and PRO2 scores for a study visit (other than Week 0) should be a maximum of 14 days prior to the day of the study visit. For study visits that include endoscopy, the final day of diary collection is the day before the subject starts bowel preparation for ileocolonoscopy.
- CDAI/PRO2 calculation will be performed using the 7 latest days of diary entry in the collection window. These days do not have to be consecutive. At least 4 of those 7 days of diary data must be collected in the final 7 days of the collection window. If either of these criteria are not met, the CDAI/PRO2 score will be counted as “missing.”

- If the requirements outlined above are not met, CDAI/PRO2 cannot be calculated for that study visit. If this occurs prior to the Week 0 visit, the subject cannot meet Inclusion Criterion 2)f), cannot be randomized, and must be screen-failed.

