10 STATISTICAL CONSIDERATIONS

10.1 Sample Size Determination

Approximately 240 subjects will be randomized into 1 of 3 treatment arms on Day 1 in a 3:3:2 ratio, resulting in approximately 90 subjects in each BMS-986165 dose arm and 60 subjects in the placebo arm. Sample size is based on the power to compare the response rates of the BMS-986165 3 mg BID treatment arm with placebo, or the BMS-986165 6 mg BID treatment arm with placebo for each of the co-primary endpoints at Week 12 (Day 85). A Bonferroni adjustment will be used to compare the BMS-986165 3 mg BID and BMS-986165 6 mg BID active treatment groups to placebo. Response rates for clinical remission and endoscopic response are based on published response rates using similar endpoints.²⁷

. With a 2-sided chi-square test at a significance level 0.025 and a sample size of 90 subjects for each BMS-986165 treatment arm and 60 subjects in the placebo arm,

Additionally, with a 2-sided chi-square test at a significance level of 0.025 and a sample size of 90 subjects for each BMS-986165 treatment arm, and 60 in the placebo arm,

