10.4.1 Co-primary Endpoint Analyses

The co-primary endpoints, the proportion of subjects achieving clinical remission at Week 12 and the proportion of subjects achieving endoscopic response at Week 12, will be analyzed separately using stratified Cochran-Mantel-Haenszel (CMH) tests stratified by geographic region (US, Japan,

[REDACTED] Differences in response rates and corresponding 2-sided 95% and 97.5% confidence intervals (CIs) will be provided along with the point estimates and corresponding 95% and 97.5% CIs for each treatment group using a binomial model. The odds ratio (odds in an active treatment group/odds in placebo), and the corresponding 2-sided 95% and 97.5% CIs will be provided as well.

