10.4.4 Secondary Endpoint Analyses

The analysis model for the binary secondary endpoints will use CMH tests [REDACTED]

[REDACTED] Differences in response rates and corresponding 2-sided 95% and 97.5% CIs will be provided along with the point estimates and corresponding 95% and 97.5% CIs for each treatment group using a binomial model. The odds ratio (odds in an active treatment group/odds in placebo), and the corresponding 2-sided 95% and 97.5% CIs will be provided as well.

The analysis model for continuous secondary endpoints will use analysis of covariance (ANCOVA) [REDACTED]

[REDACTED] baseline value will be added into the model as a covariate. Treatment differences based on least squares means and the corresponding 2-sided 95% and 97.5% CIs will be provided for the difference between each active treatment and placebo.

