10.6.4 Interim Analysis

In addition to the primary efficacy analysis conducted when 12-week data are available for all randomized subjects, interim analyses may be performed. The purpose of interim analyses will be to help in early planning for further clinical development of the compound.

To maintain the overall probability of Type I error at the specified 0.05 level, a modified Haybittle-Peto method²⁸ will be used as the alpha-spending function, which assigns $\alpha=0.001$ to each interim analysis, and the remaining alpha to the final (Week 12) analysis of the primary efficacy endpoints.

The SAP for the study will be finalized prior to any interim analysis. The details (including the timing) of the interim analyses will be provided in an Interim Analysis Plan prior to the database lock for any interim analysis. The results of the interim analyses will be reviewed by an unblinded internal BMS team that is independent of the study team responsible for the conduct of the study. The study team members, including the medical monitors and other study personnel, will remain blinded and will not have access to any unblinded interim analysis results or data until the final database lock for the Week 52 data has occurred.

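### Optional: adjusting the clinical remission test for continuous baseline CDAI could change its power by about -0.6 to +6.7 points, or by at most about +1.9 if a CDAI category is already a stratum

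*Combined protocol and SAP*

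**What the plan says.** - **Primary test.** Section 10.4.1: the co-primaries are "analyzed separately using stratified Cochran-Mantel-Haenszel (CMH) tests stratified by geographic region". The list breaks off in a redaction after its first regions. Rate differences and odds ratios are planned with 95% and 97.5% confidence intervals.
- **Endpoint.** Section 4 defines clinical remission by an absolute cut-off, CDAI below 150. Endoscopic response is relative: at least 50% "improvement from baseline in the SES-CD".
- **Baseline score.** Section 6.1, criterion 2)f, requires "CDAI score of 220 to 450 AND" further activity criteria. Under Section 9.1, a subject whose CDAI cannot be calculated before Week 0 "cannot be randomized, and must be screen-failed".
- **Adjustment elsewhere.** For the ANCOVA of continuous secondary endpoints, Section 10.4.4 says that the "baseline value will be added into the model as a covariate".
- **Randomization.** Section 7.2 describes a "computer-generated block randomization scheme and in accordance with stratification criteria" that it does not list.
- **Assumed rates.** Section 10.1: "Response rates for clinical remission and endoscopic response are based on published response rates using similar endpoints". The rates and the power are redacted.
- **Timing.** Section 10.6.4: "The SAP for the study will be finalized prior to any interim analysis".

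**The concern.** Remission depends on reaching a fixed score. A subject entering at CDAI 220 needs a fall of more than 220 - 150 = 70 points; one entering at 450 needs more than 450 - 150 = 300. Baseline CDAI may therefore predict remission, although the documents give no correlation. It is collected before treatment in everyone properly randomized, and non-responder imputation (Section 10.4.2) gives every subject in the full analysis set an outcome. Adjustment then needs no new data.

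A CMH test conditions on categories and cannot use the score as a continuous variable. With about 60 placebo subjects and alpha 0.025 per dose, some precision on one co-primary may be left unused. Endoscopic response is outside this point, because it is already measured against each subject's own baseline SES-CD.

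**Working it through.** **1. The plan's own figures.** 240 x 3/8 = 90, 90, and 240 x 2/8 = 60. Alpha: 0.025 + 0.025 = 0.05. Both agree with Sections 10.1 and 10.4.6. The stated power cannot be reproduced because it and the rates are redacted, so every rate below is an assumption.

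**2. Formula.** Take 15% (n = 60) versus 35% (n = 90).
- Pooled rate = (9 + 31.5)/150 = 0.27.
- Null SE = sqrt(0.27 x 0.73 x (1/60 + 1/90)) = 0.0740.
- Alternative SE = sqrt(0.15 x 0.85/60 + 0.35 x 0.65/90) = 0.0682.
- Power = Phi((0.20 - 2.241 x 0.0740)/0.0682) = 69.2%.

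If baseline CDAI explains a share R2 of the outcome variance, replace n by n/(1 - R2). Power becomes 70.2%, 71.8%, 74.5% and 77.3% at R2 = 0.02, 0.05, 0.10 and 0.15. Over placebo rates of 10-25% and differences of 15-25 points (base power 36-92%), the gains at those R2 values are 0.6-1.0, 1.4-2.6, 2.8-5.4 and 4.0-8.3 points. The formula ignores the cost of fitting a covariate that predicts nothing, so simulation is needed.

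**3. Simulation with an ordinary logistic (Wald) test**, three region strata, 4,000 trials per setting, CMH power then adjusted power:
- 15% versus 35%: 67.1 to 66.3% with no prognostic value; 69.7 to 69.9% at R2 about 0.02-0.04; 69.6 to 73.0% at about 0.05-0.09; 68.6 to 73.9% at about 0.08-0.14.
- 20% versus 40%: 62.8 to 62.5%, 64.2 to 64.8%, 65.5 to 69.3% and 63.5 to 70.3% at similar strengths.

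**4. Simulation of the recommended test.** This is the score test for treatment with its variance multiplied by n/(n - q), where q is the number of parameters without treatment. With three regions and CDAI, q = 4 and the factor is 150/146 = 1.027. With region x two CDAI categories and CDAI, q = 7 and it is 150/143 = 1.049.

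Assumptions: 3:3:2 allocation in blocks of 8 within strata; baseline CDAI normal (310, 60) truncated to 220-450; Week 12 CDAI linear in baseline with within-arm SD 90; remission 15% v 35%, 10% v 28% and 25% v 47% (base power about 70%) or 15% v 42% (about 92%); non-responder share 0% or 15% for the pairs with a 15% placebo rate; CDAI category cut at 300. There were 6,000-8,000 trials per setting, and the SE of each gain is at most 0.5 points. Change in power, adjusted minus CMH, in points:

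| Strata | Target | Correlation 0 | 0.3 | 0.45 |
|---|---|---|---|---|
| Region only | Remission, base about 92% | -0.1 | 1.0 to 1.2 | 2.0 to 2.7 |
| Region only | Remission, base about 70% | -0.6 to -0.1 | 1.5 to 2.6 | 4.7 to 6.7 |
| Region x CDAI category | Remission, base about 92% | -0.2 to -0.1 | 0.0 to 0.1 | 0.3 to 0.9 |
| Region x CDAI category | Remission, base about 70% | -0.5 to 0.0 | 0.6 to 0.9 | 1.0 to 1.9 |
| Region only | Both co-primaries | -0.4 to -0.1 | 0.5 to 1.2 | 1.4 to 3.6 |
| Region x CDAI category | Both co-primaries | -0.4 to 0.0 | 0.0 to 0.6 | 0.1 to 1.0 |

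The joint rows assume endoscopic power of about 70%. A further simulation of 15% versus 35% gave -0.3 / 2.6 / 5.8 (region only) and -0.1 / 0.2 / 1.3 (with the category). The 0.2 lies below the tabulated 0.6 to 0.9, a gap of the size that simulation error can produce.

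**5. Test size.** Up to correlation 0.45, type I error was 0.021-0.026 for CMH and 0.022-0.027 for the adjusted test (Monte Carlo SE 0.001). Size-adjusted gains for 15% versus 35%, region only, were -0.2 / 1.7 / 5.7, so the gain does not come from a liberal test.

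**6. Estimate.** Against an unadjusted Wald interval, the SE of the standardized risk difference was 1% larger, 1% smaller and 4-5% smaller at the three correlations. Coverage of its 97.5% interval was 96.9-97.4%. In the step 3 simulation, a test built on its simple large-sample variance had size 2.6-3.6%, which is why the score-test p-value should govern.

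**The case against.** **Nothing is wrong with the plan.** Correct. CMH is prespecified and holds its size. A reader might infer that the planned test is deficient or the trial underpowered; neither the documents nor the simulations support that.

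**The key text is redacted.** This stands. The strata and the named co-primary sensitivity analysis (Section 10.4.3) cannot be read. Section 10.4 calls itself a summary and leaves the detail to the SAP, and the Amendment 05 change table says it was aligned with an August 2022 SAP version. A reader might infer that baseline CDAI has been overlooked. That cannot be asserted: a CDAI stratum or an adjusted analysis may already exist.

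**The gain that matters is small.** Largely true. A dose succeeds only on both co-primaries, where several entries cannot be told from zero. The 6.7 points need correlation 0.45, base power of about 70% and no CDAI stratum.

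**Size is traded for power.** In part. At correlation 0.6 with remission rates of 10% and 15%, adjusted size was 0.0265 and 0.0261, against 0.0236 and 0.0239 for CMH. An F(1, n - q) reference kept size at or below 0.0251, but gains fell to -1.5 to -0.5 / 0.6 to 1.3 / 2.3 to 5.2 (region only) and -1.6 to -0.6 / -0.8 to 0.1 / 0.3 to 0.8 (with the category). The size-adjusted comparison covers one rate pair.

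**Gaps in applying it.** The full analysis set includes anyone randomized in error without a valid baseline CDAI. The simulations used 3:3:2 allocation only, not the earlier period with the 12 mg QD arm. Both points stand as limits.

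**The ANCOVA covariate proves no inconsistency.** Agreed. It shows only that the plan already uses baseline adjustment where a model is fitted.

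**Conclusion.** This is an optional efficiency gain. Whatever the redacted strata are, a CMH test cannot use baseline CDAI as a continuous variable. For correlations of 0 to 0.45, adjustment changes remission power by about -0.6 to +6.7 points with region the only stratum, and by about -0.5 to +1.9 points if a CDAI category is already a stratum. For joint success the range is about -0.4 to +3.6 points.

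The correlations, remission rates, baseline distribution, region shares and imputed share are all assumptions. A reader might take the upper end as the expected benefit; the documents give no basis for choosing any point in the range. Confidence is medium, because the sponsor can see strata and rates that we cannot.

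**What to change.** First check whether the redacted strata or the SAP already use baseline CDAI. If the gain still looks worthwhile, and before any unblinded analysis (including an interim under Section 10.6.4), write into the SAP and Section 10.4.1, for clinical remission only:

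1. For each dose versus placebo, a logistic model with treatment, the actual randomization strata and continuous baseline CDAI.
2. One fixed test, the score test with variance multiplied by n/(n - q), whose p-value governs.
3. A written rule for pooling sparse strata, based on counts combined over arms, and one for any subject without a valid baseline CDAI.
4. The standardized risk difference with 95% and 97.5% intervals, and the odds ratio labelled as conditional (model) or Mantel-Haenszel.
5. The planned CMH test as a sensitivity analysis.

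If any unblinded analysis has already occurred, keep CMH as primary and report the adjusted test as supplementary.

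**Cost:** SAP and protocol text plus modest programming; no new data. The estimator becomes model-based, and up to 0.6 points of remission power are lost if baseline CDAI is not prognostic. The p-value and the 97.5% interval disagreed in 1.1-4.6% of simulated trials; CMH with an assumed unstratified Wald interval disagreed in 1.6-5.1%.

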10.4.2 Imputation Methods for Co-primary Endpoints

Non-responder imputation (NRI) will be used for co-primary efficacy endpoints for subjects who discontinue treatment prior to Week 12 and have no Week 12 assessments after treatment discontinuation, [REDACTED] initiate use or continue to use prohibited medications in the Induction Period, require surgical procedure(s) for treatment of CD or related complications in the Induction Period, or have otherwise missing endpoint data at the Week 12 (Day 85) timepoint, ie, the NRI will be the primary method of imputation for the co-primary efficacy endpoints.

10.4.3 Sensitivity Analyses for the Co-primary Endpoints

The following sensitivity analysis will be performed on the co-primary efficacy endpoints:

[REDACTED]

Additional sensitivity analyses of the co-primary endpoints may be defined in the SAP.

10.4.4 Secondary Endpoint Analyses

The analysis model for the binary secondary endpoints will use CMH tests [REDACTED]

[REDACTED] Differences in response rates and corresponding 2-sided 95% and 97.5% CIs will be provided along with the point estimates and corresponding 95% and 97.5% CIs for each treatment group using a binomial model. The odds ratio (odds in an active treatment group/odds in placebo), and the corresponding 2-sided 95% and 97.5% CIs will be provided as well.

The analysis model for continuous secondary endpoints will use analysis of covariance (ANCOVA) [REDACTED]

[REDACTED] baseline value will be added into the model as a covariate. Treatment differences based on least squares means and the corresponding 2-sided 95% and 97.5% CIs will be provided for the difference between each active treatment and placebo.

10.4.5 Imputation Methods for Secondary Endpoints

NRI will be used for subjects who discontinue treatment prior to Week 12 and have no Week 12 assessments after treatment discontinuation. [REDACTED]

[REDACTED] initiate use or continue to use prohibited medications in the Induction Period, require surgical procedure(s) for treatment of CD of related complications in the Induction Period, or have otherwise missing endpoint data at the specified timepoint for binary endpoints.

For continuous secondary efficacy endpoints, a multiple imputation (MI) analysis will be used for subjects who discontinue study treatment prior to Week 12 and have no Week 12 assessments after treatment discontinuation, and for subjects who require a protocol-prohibited medication/therapy/surgical procedure that could improve the disease prior to the Week 12 endpoint, or who have otherwise missing endpoint data at the specified time point for continuous endpoints.

10.4.6 Adjustment for Multiplicity of Co-primary and Secondary Endpoints

Alpha will be split in 2 separate testing branches at a 2-sided $\alpha=0.025$ for BMS-986165 3 mg BID compared to placebo and BMS-986165 6 mg BID compared to placebo. The testing order of co-primary and secondary endpoints will be tested in the sequence shown in [Table 18](#).

Table 18: Testing Order of Co-primary and Secondary Endpoints

BMS-986165 3 mg BID Comparisons to Placebo (alpha=0.025)	BMS-986165 6 mg BID Comparisons to Placebo (alpha=0.025)
Co-primary Endpoints	
Clinical remission at Week 12 Endoscopic response at Week 12	Clinical remission at Week 12 Endoscopic response at Week 12
Secondary Endpoints	
1. Clinical response at Week 12	1. Clinical response at Week 12
2. PRO2 remission at Week 12	2. PRO2 remission at Week 12
3. Change from baseline in SES-CD at Week 12	3. Change from baseline in SES-CD at Week 12

There will be no multiplicity adjustment for any other endpoints including exploratory efficacy endpoints; however, nominal p-values will be provided as descriptive statistics.

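### The two dose branches are fixed at 0.025 with no transfer of alpha; passing on the alpha of a fully successful branch would add power for the other dose within the same 0.05 limit

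*Combined protocol and SAP*

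**What the plan says.** Section 10.1 sets the principle: "A Bonferroni adjustment will be used to compare the BMS-986165 3 mg BID and BMS-986165 6 mg BID active treatment groups to placebo". It sizes the trial to match: "With a 2-sided chi-square test at a significance level 0.025 and a sample size of 90 subjects for each BMS-986165 treatment arm", with 60 on placebo.

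Section 10.4.6 carries this into the testing plan: "Alpha will be split in 2 separate testing branches at a 2-sided" level of 0.025 for each dose against placebo. On order it says: "The testing order of co-primary and secondary endpoints will be tested in the sequence shown in" Table 18. Each column of that table lists clinical remission and endoscopic response as co-primaries, then clinical response, PRO2 remission and, as the last entry, "3. Change from baseline in SES-CD at Week 12". Nothing follows that step, and the section has no rule linking the two columns.

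Section 10.4.1 plans intervals at two levels: "Differences in response rates and corresponding 2-sided 95% and 97.5% confidence intervals (CIs) will be provided along with the point estimates". Section 10.4.4 does the same for the secondary endpoints.

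Section 10.6.4 states the overall limit: "To maintain the overall probability of Type I error at the specified 0.05 level". It assigns 0.001 to each optional interim analysis "and the remaining alpha to the final (Week 12) analysis of the primary efficacy endpoints".

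**The concern.** With two separate branches, each dose keeps its own 0.025 to the end. If one dose is rejected on all five endpoints, its 0.025 has done its work and could be used again, but the plan lets it lapse. The other dose is still judged at 0.025 although only one branch then remains open to error.

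The trial is described as dose-ranging and both doses are compared with a single placebo group of 60, so whether the second dose is also formally positive is a real question. At stake is power for that second dose. Control of error is not in doubt.

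A smaller matter sits alongside. Table 18 gives 0.025 per branch, which is the level when no interim analysis spends alpha. Section 10.6.4 leaves less than 0.05 for Week 12 if one does, and no section states the per-dose level that results.

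**Working it through.** **The plan's own figures.** Two branches at 0.025 sum to 0.025 + 0.025 = 0.05, the limit in Section 10.6.4. Allocating 240 subjects 3:3:2 gives 90, 90 and 60. Both reproduce exactly. The planned power cannot be reproduced because the rates and power are redacted.

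**The alternative rule.** Each branch starts at 0.025 in the Table 18 order, with both co-primaries required before the secondaries and testing stopped at the first failure. If all five tests in one branch are rejected, the other branch is tested in the same order at 0.025 + 0.025 = 0.05.

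**Why error stays at or below 0.05.** Within a branch, a false rejection requires rejecting the first true null in the order, so its probability is at most the branch level.
- *Both branches contain a true null.* Alpha can be released only by a branch that has already made a false rejection at 0.025. The error event is therefore the same as under the fixed split, with probability at most 0.025 + 0.025 = 0.05.
- *Only one branch contains a true null.* That branch is tested at 0.05 at most, so the error is at most 0.05.

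**Why nothing is lost.** A branch is never tested below 0.025, so every fixed-split rejection remains. Release happens only after one dose has already succeeded, so the chance of at least one success cannot change.

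**Simulation inputs.** Ten normal test statistics (2 doses × 5 endpoints). The correlation between doses on the same endpoint follows from the shared placebo group: 90/(90 + 60) = 0.6. The correlation between endpoints is assumed to be 0.4, which gives 0.6 × 0.4 = 0.24 across doses and endpoints. Power is per test at two-sided 0.025, with mean z(0.9875) + z(power). Success means both co-primaries rejected. There were 1,000,000 draws.

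The effect on a single test shows the mechanism. At 80% power the mean is 2.241 + 0.842 = 3.083; at 0.05 the power is Φ(3.083 − 1.960) = Φ(1.123) ≈ 87%. At 70% it is Φ(2.241 + 0.524 − 1.960) = Φ(0.805) ≈ 79%.

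**Error check** (fixed split, then transfer):
- One dose fully effective, one null co-primary in the other: 0.025, then 0.050.
- One null co-primary in each dose: 0.045 under both.
- Global null: 0.005 under both.

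**Case 1: both doses at 80% per co-primary.**

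| Power of secondaries | A given dose releases alpha | Per-dose success | Both doses succeed |
|---|---|---|---|
| 80% | 47.7% | 67.7% → 71.3% | 53.8% → 61.1% |
| 60% | 28.3% | 67.7% → 69.6% | 53.8% → 57.7% |
| 50% | 20.1% | 67.7% → 68.9% | 53.8% → 56.4% |

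At least one dose succeeds in 81.5% of trials before and after. The table agrees to rounding: 67.7 + 67.7 − 53.8 = 81.6 before, and 71.3 + 71.3 − 61.1 = 81.5 after.

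**Case 2: 6 mg at 90%, 3 mg at 70% per co-primary.**

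| Power of secondaries (6 mg / 3 mg) | 3 mg success | Gain |
|---|---|---|
| 90% / 70% | 54.2% → 62.2% | 8.0 points |
| 80% / 60% | 54.2% → 60.3% | 6.1 points |
| 60% / 50% | 54.2% → 57.3% | 3.1 points |

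At least one dose succeeds in 86.1% of trials before and after.

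**Sensitivity.** With the endpoint correlation between 0.2 and 0.6, the gain runs from 1.1 to 3.9 points per dose in case 1 and from 2.9 to 8.0 points for 3 mg in case 2. A separate simulation at correlations 0.3 and 0.6, with all five tests in a branch at equal power, gave about 2 to 8 points for the weaker dose. In it the largest error under transfer was 0.050, and no fixed-split rejection was lost.

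**Interim point.** After one alpha-spending interim, the remaining-alpha rule gives (0.05 − 0.001)/2 = 0.0245 per branch; after two, (0.05 − 0.002)/2 = 0.024. Leaving Table 18 at 0.025 makes the nominal sum 0.051. Simulated single-endpoint error, with one look at information 0.3, 0.5 or 0.7, 0.0005 per dose and 4,000,000 draws:
- No interim: 0.0448.
- Final level 0.025: 0.0453 to 0.0454.
- Final level 0.0245: 0.0439 to 0.0445.

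Using 0.0245 lowers per-dose co-primary success in case 1 by about 0.4 points.

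**The case against.** The strongest reply is that nothing is broken. A fixed Bonferroni split is an accepted choice, the trial was sized on it, and this is Phase 2. The gain is only a formal result for the second dose, it needs a clean sweep of five tests by the first, and no section ties a development decision to both doses being significant. The 95% interval for each dose will be reported anyway. This is right about importance and is why the point is a recommendation. It does not make the unused alpha useful.

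The size is uncertain because every power and endpoint correlation is assumed. That stands. With co-primaries at 80% and secondaries at only 40%, alpha is released by a given dose in about 13% of trials and per-dose success moves only from 67.6% to 68.4%.

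The gain is not costless in one sense: where one dose works fully and the other has one null co-primary, error rises from 0.025 to 0.050. That is the limit the protocol sets, and it is not exceeded. The reported intervals would also cease to form a Bonferroni simultaneous set.

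On the interim point, the analyses are optional, their details are left to an Interim Analysis Plan, and Section 10.6.4 does not say whether each 0.001 is per dose or shared. Under the fixed split no error above 0.05 was shown. All of this stands, so the point is minor. Exact bookkeeping matters more once transfer is allowed, because transfer can use the full 0.05.

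Finally, Section 10.4 describes itself as a summary and leaves detail to the SAP. If the SAP already has a transfer rule, the main point falls away; none appears in the text reviewed.

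**Conclusion.** The concern holds as a missed efficiency. The fixed split is valid and consistent with Section 10.1, but it is uniformly less powerful than a whole-branch transfer that respects the same 0.05 limit. Under the main assumed scenarios the gain is about 1 to 4 points of co-primary success per dose when the doses are equally effective, and about 3 to 8 points for the weaker dose when they are not. It can be smaller if the secondaries are poorly powered. The chance that at least one dose succeeds is unaffected.

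The validity of the transfer follows from the argument above and not from the assumed powers. It does require that both co-primaries be rejected before the secondaries and that testing stop at the first failure. Table 18 implies this, but Section 10.4.6 does not say so outright. The missing per-dose level after an interim analysis is a minor gap in wording.

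**What to change.** Define A = 0.05 − 0.001k, where k is the number of interim analyses that spend alpha under Section 10.6.4 and each 0.001 is shared across the two doses; A = 0.05 if there are none. Then state in Section 10.4.6 and in the SAP:

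> *Each branch is tested at two-sided A/2 in the Table 18 order. Both co-primaries must be rejected before the secondaries are tested, and testing stops at the first failure. If all hypotheses in one branch are rejected, its alpha passes to the other branch, which is then tested in the same order at two-sided A.*

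Report intervals at the levels used, 1 − A/2 and 1 − A. With k = 0 these are the 97.5% and 95% intervals already planned. With k = 1 they are 1 − 0.0245 = 97.55% and 1 − 0.049 = 95.1%. The same text brings Table 18 into line with Section 10.6.4.

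The cost is protocol and SAP wording, with the approvals that an amendment needs. No patients or data are added. The rule must be fixed before the Week 12 unblinding and before any earlier unblinded interim analysis.
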